The flowchart of the study is presented in Figure 1. Randomization was carried out among the 23 priority districts in this study with a ratio of 2:1 (that is, 2 intervention districts per 1 control district). The details of randomization are explained in section B.4 of this document. **The assigned 15 intervention districts and 8 comparison districts** are described in Table 6. Potential participants in the intervention area will be screened through the inclusion and exclusion criteria established for

this study. The criteria for participants who are eligible for this study are explained in section B.3 of this document and Annex2.

According to the Indonesian Ministry of Health's current recommendation, HIV blood test at an authorized health facility is still the current practice for HIV diagnosis. Both participants in the intervention and comparison area will be offered for HIV blood test at a health facility. Participants in comparison areas and participants in intervention areas who agree to take HIV test at a health facility will then be managed further according to the existing guideline or "standard of care." For participants in intervention areas who refuses to have her blood drawn for HIV test at a health facility will then be offered self-testing using OraQuick®. Participants will then fill and sign the informed consent to participate in CBS study.

Next, participants will be offered to do the test assisted or unassisted. If the participant chooses to perform the test assisted, the PL/PE will help her from filling in a baseline survey, performing the test, and filling in a post-test survey. If the participant chooses to perform the test unassisted, there will be two options for the participant to get the test kit. First, PL/PE will deliver the test kit for the participant, help with filling in the baseline survey on the spot and give information about uploading test results and the post-test survey, along with a hotline number to call for any questions and concerns, including follow-up steps after participants have received the results. The second method, participants will be given a link online which will entitle information of this study, eligibility criteria, informed consent, baseline survey, link to order a test kit, link to upload result and link to fill in the post-test survey. Participant who chooses this second method will also be given hotline number should there be any further inquiries.

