Sample size requirements for the third question measurement pertains to the number of FSW who test positive for HIV at a health facility and are thus eligible to initiate treatment. This will depend upon (1) the number of FSW presenting at health facilities for testing and (2) the positivity rate among those tested. Sample sizes should thus be calculated accordingly. If we assume a testing positivity rate of 3%, it is apparent that the expected number of FSWs who would be eligible for treatment will be small and we will lack sufficient statistical power to make meaningful comparisons with comparison districts. For this reason, it is recommended that the impact of community screening among FSW be measured using SIHA data for FSW in both intervention and comparison districts. This estimate of impact derived in this way will be confounded if it were to be the case that interventions other than HIV self-testing were to be better implemented in intervention vs. comparison districts. It might be possible to minimize this potential bias by including measures of intervention implementation performance in the intervention and comparison districts in multivariable analyses. Thus, a large enough sample size is required to ensure sufficient power to determine the difference in the intervention and control districts.

C. THE INTERVENTION

1. General Description of The Intervention

FSW who meet the eligibility criteria will be offered for HIV blood test first. Participants who wish to take the test will then managed according to the current guideline for standard of care. Participants who disagree to take HIV blood test will then be offered screening test with Ora-Quick®. There will be with two options for community HIV screening by Peer Leaders: (1) in a convenient community setting assisted by PL/PE (assisted screening) or (2) in a setting of their own choosing without assistance from PL/PE (unassisted screening). FSW will also be able to access a community-based screening test by following online link from messages spread through WhatsApp number without having to come into contact with outreach workers. The saliva-based Ora-Quick® test kit will be used for community screening.

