A short baseline survey will be conducted at the time of initial outreach contact with FSW during the study period. The purpose of the baseline survey is to collect background information on FSW that may be used to assess whether FSW with different characteristics are more or less amenable to community HIV screening and HIV testing at health facilities. An application will be developed so that the survey can be completed and submitted to a server using mobile phones PL/PE/FSW. The following basic information will be gathered (see draft questionnaires for the baseline and post-test surveys in the annex of this protocol).

- Name (full name/initial)
- Age
- Date of birth

- Test Kit ID Number
- Education
- Marital status
- Age at initiation of sex work
- Number of clients last seven (7) days
- Methods of clients' recruitment (fixed facility, street, internet, online platform)
- Consistency of condom use
- Ever been tested for HIV
- When last time tested
- Ever been diagnosed with an STI (other than HIV)

In addition to these questions, FSW will be asked twelve (12) questions in the short version of anticipated HIV stigma scale (Reinius et al., 2017) designed to measure the extent to which participants anticipated negative intrapersonal and interpersonal consequences were they to contract HIV in the future. During data analysis, we will assess the ability of an index constructed from the data items collected to predict which FSW presented at health facilities for formal HIV testing. This will provide an estimate of the impact of anticipated stigma on HIV testing among FSW in Indonesia.

2. Post-test Survey

A short post-test survey will be conducted after the test has been taken. The purpose of post-test survey is to collect information of the experience of clients using the test kit and to record the test result. Some inquiries will be presented on a scale of 1-5, some inquiries will have binary answers (Yes/No, Reactive/Non-Reactive). The following inquiries will be made:

- The clarity of information being provided (flier or short video), on a scale of 1-5
- The easiness of test procedure, on a scale of 1-5
- Perceived accuracy of the test result, on a scale of 1-5
- The quality of response by the assigned contact person/hotline, on a scale of 1-5
- Clients' acceptance/perception towards the study procedure
- The likelihood of clients to recommend their peers to take the test, on a scale of 1-5
- Test result

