In the event that participants' data are collected by paper, a procedure to upload the data into the established online system will be developed. Each data manager in the IUs needs to conduct the procedure regularly. This is to ensure that all data are being captured thoroughly.

F. DATA ANALYSES

The data analyses to be undertaken will be directed to addressing the research questions laid out at the beginning of the protocol and statistical tests appropriate to each specific analysis will be performed to inform the interpretation of results. The specific steps in the data analysis will be as follows:

1. Compare the characteristics of FSWs who receive self-testing and blood testing.

2. Compare the characteristics of FSWs who receive assisted and unassisted self-testing.
3. Compare proportion of FSWs taking confirmatory test out of those who receive the test in the assisted and unassisted self-testing.
4. Compare the proportion of FSWs who receive HIV test out of those who got offered for the test (including self-testing) in the intervention group with proportion of FSWs who receive HIV test in the control group.
5. Compare the proportion of FSWs taking confirmatory test (including self-testing) out of those receive the test in intervention groups and control group.
6. Compare the proportion of HIV positive in the assisted, unassisted (intervention) and HIV positive in the control group.
7. Compare the proportion of ART initiation in the assisted, unassisted (intervention) and the control group.
8. Calculate the cascade of HIV testing and treatment.
9. Compare stigma scores and FSWs who went to a health facility for HIV testing between assisted, unassisted group.
10. Compare the HIV and STI risk behaviors between assisted and unassisted group.

G. CONTINGENCY STUDY DESIGN

Should the OraQuick® test kits not become available in sufficient time to conduct a full-scale cRCT, a smaller-scale study will instead be undertaken. The purpose of the smaller study is the same as the cRCT described above, and the same protocol described above will be implemented. But the comparison is achieved targets between before and after intervention – there will be no comparison districts. The study will be undertaken in three (3) districts. The three districts will be selected from different parts of Indonesia, and they are: Kota Bandung (west part of Indonesia), Kota Denpasar (central part of Indonesia), and Kota Makassar (center-east part of Indonesia).

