Annex 1. Flowchart of Routine Data Recording

Annex 2. Eligibility Form

Eligibility Participants Form for Intervention

To be completed by PL/PE during FSW outreach

These checklists are to be completed by PL/PE during FSW outreach to assess the eligibility of FSW to participate in this study. If questions number 1-7 is answered “Yes”, then participant is eligible for the study. If question number 8 is answered “Yes”, then participant is not eligible for the study, but eligible for “blood test study in health facility”.

No	Criteria inclusion	Yes	No
1	Female, aged 18 years old or more		
2	Admit having transactional sex (vaginal, oral, or anal) at least once within the last one month		
3	Have never had any HIV test taken within the last 6 months		
4	Self-reported HIV Negative OR HIV status unknown		
5	Agreed to participate in this study		
6	Not currently participating in any other HIV prevention study		
7	After being offered for HIV testing in health facility, participant stated: A. Agree for HIV testing in health facility* B. Not agree for HIV testing in health facility**		

Note:

* Use information form for VCT

** Use information form for OFT

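### Step 9 of Section F examines stigma only among self-screened women, so it cannot deliver the estimate of stigma's influence on facility testing that Section E.1 promises

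*Combined protocol and SAP*

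**What the plan says.** Section E.1 adds twelve anticipated-stigma items to the baseline survey. An index built from them will be assessed for its ability to "predict which FSW presented at health facilities for formal HIV testing". The section then states its purpose: "This will provide an estimate of the impact of anticipated stigma on HIV testing among FSW in Indonesia". Neither sentence limits the analysis to women who self-screen.

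Section F, step 9, is the only step listed for the cluster trial that mentions stigma: "Compare stigma scores and FSWs who went to a health facility for HIV testing between assisted, unassisted group".

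Section C.1 says how women reach those two groups: "Participants who disagree to take HIV blood test will then be offered screening test with Ora-Quick". Section B.1 and item b of Section C.2 give the same order. Section C.1 also describes an online route, by "online link from messages spread through WhatsApp number without having to come into contact with outreach workers".

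On timing, Section E.1 says: "A short baseline survey will be conducted at the time of initial outreach contact with FSW during the study period". Section B.1 puts the survey later, after refusal of the blood test, the OraQuick offer, consent and the choice of method: "If the participant chooses to perform the test assisted, the PL/PE will help her from filling in a baseline survey". Item 7 of the eligibility form in Annex 2 has two branches. A woman who agrees to facility testing gets the note "Use information form for VCT", and a woman who does not agree is sent to the oral-fluid equivalent.

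**The concern.** The promised quantity concerns who goes to a health facility for testing. On the outreach route, the women in step 9 are selected by their first answer to exactly that question. Those who said yes are left out, although they answer the same stigma items in Annex 4 and Annex 5 records whether they then attended.

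The protocol's background section presents stigma as a barrier to testing and self-testing as a way round it. If stigma works mainly by making women decline the first facility offer, most of its effect has occurred before step 9 begins. A comparison among women who declined could then show little or no association, and could be misread as evidence that stigma has little to do with facility testing.

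**Working it through.** The plan states no figure for the stigma analysis, so there is none to reproduce. The check has three parts.

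**1. Data against analysis.**
- Facility-test acceptors: stigma items in Annex 4, attendance in Annex 5 (to be validated at the facility). Not in step 9.
- Self-screened women: baseline survey in Annex 6. Later facility testing is recorded under Section E.3 and varies within the group. In step 9.
- Women who decline both tests: item c of Section C.2 gives them a reminder and a later offer and mentions no survey. Section E.1's timing would include them; the order in B.1 and the two branches in Annex 2 suggest otherwise.

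Step 9 therefore uses only part of the women for whom both score and outcome are planned.

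**2. Simple illustration (all inputs assumed).** First-offer acceptance is 60% with low stigma and 40% with high stigma. All decliners screen, and 30% of them later attend whatever their stigma. Let r be the share of acceptors who attend. Overall attendance = acceptance × r + (1 − acceptance) × 0.30.
- r = 100%: 0.60 + 0.40 × 0.30 = 0.72 against 0.40 + 0.60 × 0.30 = 0.58; ratio 0.81.
- r = 80%: 0.48 + 0.12 = 0.60 against 0.32 + 0.18 = 0.50; ratio 0.83.
- r = 50%: 0.30 + 0.12 = 0.42 against 0.20 + 0.18 = 0.38; ratio 0.90.

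Among decliners it is 30% against 30% throughout, ratio 1.00, because that was assumed. This shows a mechanism and does not forecast a result.

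**3. Simulation (all inputs assumed; 400,000 women per setting).** S is the standardised stigma score and U an unmeasured willingness to test.
- logit P(accept facility test) = bS + gU, with b = −0.3 or −0.7 and g = 0 or 1; 80% of acceptors attend.
- logit P(accept screening, if declined) = 0.8 + cS + gU, with c = −0.5, 0 or +0.5.
- logit P(attend later, if screened) = −1 + gU when stigma acts on the first decision only, or −1 + bS + gU when it acts equally on the later visit.

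Odds ratio per standard deviation of stigma for facility attendance, range over 12 settings:

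| Stigma acts on | All women offered | Annex 4 and Annex 6 women | Self-screened only |
|---|---|---|---|
| First decision only | 0.62–0.90 | 0.67–0.98 | 0.98–1.18 |
| First decision and later visit equally | 0.52–0.85 | 0.53–0.91 | 0.49–0.85 |

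Setting by setting, the self-screened result departs from the all-women result by at most 1.18 − 0.69 = 0.49 in the first case and 0.85 − 0.75 = 0.10 in the second. The combined sample departs by at most 0.98 − 0.83 = 0.15 and 0.91 − 0.78 = 0.13. What remains in the combined sample comes mainly from women who decline both tests (14% to 22% here). It pulls the ratio towards 1 when stigma lowers screening uptake and away from 1 when stigma raises it.

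**The case against.** The strongest reply is that E.1 is itself an analysis commitment and is not restricted to self-screeners. Annex 4 collects the items from facility-test acceptors, step 1 of Section F compares self-tested with blood-tested women, and the matching step 9 of the contingency design in Section G has no assisted/unassisted limit. This stands to the extent that a reader should not infer that the whole stigma plan is confined to self-screened women. The defect is that the one listed step does not carry out E.1. Step 1 does not fill the gap, because it names neither stigma as predictor nor facility attendance as outcome.

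Four stronger readings are tempting, and the documents do not support them.
- A reader might infer that step 9 conditions on the outcome. Selection is on an initial refusal. Attendance still varies among screened women (E.3) and among acceptors (Annex 5).
- A reader might infer that every woman in step 9 has refused a facility test. That is clear for outreach. For the online route, B.1 and item c of Section C.3 list no prior facility offer, while C.1 and the additional unassisted list in E.3 imply one.
- A reader might infer that women who decline both tests certainly have no stigma score. This is deduced from form routing and conflicts with E.1. Section C.5 pays for the baseline survey separately from any test, and the study and recording flowcharts are not available to settle it.
- A reader might infer that the trial will report no stigma effect. That is one scenario. If stigma acts equally on the later visit, step 9 comes close to the all-women value. When stigma also lowers screening uptake, step 9 is then closer to it than the combined sample (for example 0.74 against 0.84, where all women give 0.73).

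**Conclusion.** The point holds as a mismatch between E.1 and step 9. Comparing assisted with unassisted women, who on the outreach route were selected by declining a facility test, cannot estimate how stigma predicts facility attendance among women offered testing, and it leaves planned data unused.

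The size is not known. Under the assumptions shown, the association disappears or reverses if stigma acts only on the first decision, and the bias is small if it acts equally on the later visit. The documents give no figures to choose between these. The case for widening step 9 is that it answers the question E.1 asks and limits the worst error (0.15 against 0.49 on the odds-ratio scale in these settings). It does not remove all bias.

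Stigma is in none of the five primary or two secondary objectives, so no main conclusion of the trial depends on this. It is nevertheless an explicitly promised result, and the main correction is easy.

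**What to change.** 1. Rewrite step 9 as one model in all women with a baseline survey, Annex 4 and Annex 6 combined. The outcome is verified attendance for HIV testing at a health facility, either first or after screening; the predictor is the stigma score. Keep assisted versus unassisted as a secondary description. This needs no new questionnaire data. The outcome record should be confirmed for every screened woman: the main table in E.3 counts later facility testing only after a reactive screen, and only the additional unassisted list counts it after any result.

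2. Reconcile the survey timing in E.1 with the order in B.1 and the branches in Annex 2, and state whether women who decline both tests are surveyed. This is a text change.

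3. Unless they are surveyed, report the result as an association among surveyed women and drop the claim about impact among FSW in Indonesia.

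Moving the survey ahead of the test offer, so as to keep answers from women who then decline both tests, is not put forward as a cheap change. It would come before agreement to participate (item 5 of Annex 2), consent would have to move earlier, and asking about stigma just before the offer could affect test uptake.

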13	Kab. Tangerang	1	391
14	Kota Bogor	2	374
15	Kota Jayapura	4	323
16	Kota Bandar Lampung	1	319
17	Kota Depok	2	287
18	Kota Malang	3	243
19	Kota Tangerang Selatan	1	184
20	Kota Bekasi	2	158
21	Kota Surakarta	2	144
22	Kota Semarang	2	129
23	Kab. Deli Serdang	1	80

Table 5. Achieved target of outreach per year in 23 priority districts (2018-2019)

No.	Kab/Kota	Region	Achieved target of outreach per year
1	Kota Denpasar	3	5100
2	Kota Jakarta Barat	1	4947
3	Kota Jakarta Pusat	1	4004
4	Kota Palembang	1	3741
5	Kota Surabaya	3	3510
6	Kota Jakarta Timur	1	3157
7	Kota Jakarta Utara	1	3129
8	Kota Jakarta Selatan	1	2905
9	Kota Medan	1	2858
10	Kota Makassar	3	2683
11	Kota Bandung	2	2164
12	Kota Bogor	2	1961
13	Kota Bandar Lampung	1	1933
14	Kabupaten Tangerang	1	1374
15	Kota Semarang	2	1317
16	Kota Sorong	4	1220
17	Kota Surakarta	2	1190
18	Kota Depok	2	1107
19	Kota Tangerang Selatan	1	994
20	Kota Jayapura	4	983
21	Kabupaten Deli Serdang	1	939
22	Kota Bekasi	2	879
23	Kota Malang	3	877

2. Study Period

The study timeline is presented below. The study will be conducted from February 2020 to November 2020 (10 months). The preparatory activities will be conducted in February to March 2020. **The intervention will be implemented from April – October 2020 (7 months)**, with the last one months of 2020 allocated for data analysis, report writing and a workshop presenting study findings.

Study timeline

Activities	Month									
	Feb	March	April	May	June	July	Aug	Sept	Oct	Nov
1. Study preparation										

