The primary limitations of the smaller-scale study are (1) the districts were not randomly chosen and (2) the proportion of HIV testing before and after intervention that might not sufficient to produce a statistically significant result to prove the success of the intervention. This smaller-scale version of the study should be viewed as a demonstration or pilot project leading to a bigger study afterwards.

Data analysis will be done by comparing changes in outcome variables measured against results in the four semesters prior to the study in the 3 districts compared to the other 20 acceleration districts.

Analysis of outcome variables are similar with the cRCT approach as below:

1. Compare the characteristics of FSWs who receive self-testing and blood testing in 3 districts.
2. Compare the characteristics of FSWs who receive assisted and unassisted self-testing 3 districts.
3. Compare proportion of FSWs taking confirmatory test in the assisted and unassisted self-testing 3 districts.

4. Compare the proportion of FSWs who receive HIV test including self-testing in the intervention group with proportion of FSW who receive HIV test in the control group (in 3 districts before the intervention and other 20 acceleration districts).
5. Compare the proportion of FSWs taking confirmatory test (including self-testing) in the intervention group with proportion of FSW who receive HIV test in the control group (in 3 districts before the intervention and the other 20 acceleration districts).
6. Compare the proportion of HIV positive in 3 districts (assisted and unassisted) and HIV positive in the control group (in 3 districts before the intervention and other 20 acceleration districts).
7. Compare the proportion of ART initiation in 3 districts (assisted and unassisted) and the control group (in 3 districts before the intervention and other 20 acceleration districts).
8. Calculate the cascade of HIV testing and treatment.
9. Compare stigma scores and FSW who went to a health facility for HIV testing.
10. Compare the HIV and STI risk behaviors.

H. RESEARCH ETHICS AND PERMISSION

[figure not shown]

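### Section G denies having comparison districts, then uses them in two different ways; read as a pooled comparison of levels, a zero effect on testing could appear as roughly a 10-point gain

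*Combined protocol and SAP*

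**What the plan says.** Section G applies if test kits arrive too late for the full cluster trial. It names three districts: Bandung, Denpasar and Makassar. It describes the comparison in three ways.

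- **Opening paragraph:** targets achieved after the intervention are compared with those achieved before it, and "there will be no comparison districts".
- **Data-analysis sentence:** changes in outcomes are "measured against results in the four semesters prior to the study in the 3 districts compared to the other 20 acceleration districts".
- **Steps 4 to 7:** proportions in the intervention districts are set against a "control group (in 3 districts before the intervention and other 20 acceleration districts").

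The section gives no model, weighting, sample size or expected effect. It does not say whether the two comparators in steps 4 to 7 are pooled, used separately, or combined as a difference of changes. It concedes that the districts were not chosen at random, but does not say that they start from a different testing level.

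**The concern.** The three descriptions are different estimands. The first uses only the 3 districts' own history. The second is a change-against-change contrast, in which a stable gap between districts cancels. The third, as worded, compares levels of proportions, so any standing difference between the 3 districts and the other 20 becomes part of the apparent effect. Steps 4 to 7 are the itemised outcome analyses, so an analyst is likely to follow them.

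The choice could also be made after the data are seen. The fallback is a live option, because Section A.5 says kit procurement is already delayed. Section G gives the fallback the same purpose as the full trial, which Section B.5 sizes for a 10-point difference.

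Step 5 has a further fault. It sets the proportion taking a confirmatory test in the intervention group against the proportion receiving an HIV test in the control group, and these are different quantities.

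**Working it through.** Section G states no figure of its own to reproduce. The check asks what each reading would show if every district simply stayed at its 2018-2019 level, that is, with no effect.

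**Inputs**

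| | Tests per semester (Table 4) | Outreach per year (Table 5) |
|---|---|---|
| Denpasar | 982 | 5,100 |
| Makassar | 866 | 2,683 |
| Bandung | 487 | 2,164 |
| 3 districts | 2,335 | 9,947 |
| Other 20 | 7,440 | 43,025 |
| All 23 | 9,775 | 52,972 |

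**Proxy for the testing proportion:** 2 × tests per semester / outreach per year.

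- 3 districts: 2 × 2,335 / 9,947 = 4,670 / 9,947 = 46.9%
- Other 20: 2 × 7,440 / 43,025 = 14,880 / 43,025 = 34.6%
- Pooled control (the 3 districts' past plus the other 20): 19,550 / 52,972 = 36.9%

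**Apparent gain in step 4 at zero effect, by reading**

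- Levels against the pooled control: 46.9 − 36.9 = 10.0 points (9.9 with unweighted district means)
- Levels against the other 20 only: 12.4 points before rounding of the two rates (11.4 unweighted)
- Before-after in the 3 districts: 0
- Difference-in-differences with a stable gap: 0

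**Sensitivity to weighting.** Suppose the 3 districts contribute two years of history (four semesters) and the other 20 contribute one year. The pooled control is then (2 × 4,670 + 14,880) / (2 × 9,947 + 43,025) = 24,220 / 62,919 = 38.5%, and the gap is 8.5 points.

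**Sensitivity to denominator**

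- One semester's tests over annual outreach: 5.0 points against the pooled control.
- Tests over the P3 semester target (Table 3): the 3 districts are at 2,335 / 3,433 = 68.0%. The other 20 are at 7,440 / 13,879 = 53.6%, a gap of 14.4 points. All 23 are at 9,775 / 17,312 = 56.5%, a gap of 11.6 points before rounding.
- The same target-based ratio as unweighted district means: 0.8 points against all 23. Malang alone stands at 243 / 84 = 289% of target and pulls the average up.

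Across these readings the no-effect result runs from 0 to about 14 points.

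**The case against.** The strongest reply is that the data-analysis sentence comes before the itemised steps and speaks of changes. Read as governing them, it makes the plan a difference-in-differences, and a stable gap does no harm. The bracket in steps 4 to 7 could also name two separate comparators. Section G further describes itself as a pilot and admits the non-random choice of districts. This stands in part: the 10 points are one outcome of an unresolved text. It does not remove the contradiction, because steps 4 to 7 mention proportions and not changes, and the opening paragraph denies the comparator altogether.

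The proxy is also open to challenge. Section F, step 4, uses women offered a test as its denominator, not women reached. One test is counted per woman per six months, so doubling a semester's tests can count a woman twice. On this proxy Denpasar is unremarkable: 38.5%, 10th of 23, although it ranks first on test volume. These points stand, and are why the figure is given as a range.

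A reader might infer three stronger things that the documents do not support.

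- **That a zero effect necessarily shows as 10 points.** This needs pooled comparators, a comparison of levels and the proxy above. The plan states none of the three as its rule.
- **That a 7-month window set against 6-month semesters adds a further 7/6.** The 7 months in Section B.2 are the full trial's timeline. Section A.5 says the fallback can be run in a shorter time and gives no length. Steps 4 to 7 use proportions, which a longer count does not by itself inflate.
- **That the three districts must be re-drawn because Table 6 allocates Bandung and Makassar to Comparison.** That allocation has no force if the full trial is not run. Section G chose the districts to cover different parts of the country, and changing sites is a separate decision.

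**Conclusion.** The contradiction is real and needs correcting before the fallback is used. Followed as a pooled comparison of levels, steps 4 to 7 carry the baseline difference between districts into the estimate. For step 4 that could be roughly 10 points at zero effect, as large as the difference for which the full trial was sized. The defensible range is about 0 to 14 points.

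The figure assumes that 2018-2019 levels persist and that tests over outreach approximates the testing proportion. Tables 4 and 5 speak only to testing. They give no size for confirmatory testing, positivity or ART initiation (steps 5 to 7), where the structural fault is present but not quantified. The point matters only if the contingency design is adopted.

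**What to change.** 1. Delete the statement that there are no comparison districts.
2. Rewrite steps 4, 6 and 7 as one difference-in-differences: the intervention-period value minus the mean of the four prior semesters in the 3 districts, minus the same change in the other 20. Make the district the unit of analysis.
3. State one denominator for each outcome and use it in both periods and both groups. It must be one that was recorded in the prior semesters. Express any counts per month.
4. In step 5, compare the same quantity on both sides. Report confirmatory testing after self-testing descriptively within the 3 districts, because it has no pre-period there.

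The cost is mainly rewording. The four-semester history and the 20-district comparison are already named in Section G, although Tables 4 and 5 show history only for tests and outreach, so the source for positivity and ART initiation should be confirmed. The statistical price is a wider interval with only 3 treated districts. The estimate also depends on the two groups of districts having moved in parallel without the intervention, which should be stated as an assumption.
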